### 8.3 Accountability and Destruction of All Study Medication

Drug supplies will be counted and reconciled at the site before being returned to Santen or designee or being destroyed by the site.

The investigator or designee must ensure that the study medication is used in accordance with the approved protocol and is dispensed only to patients enrolled in the study. To document appropriate use of study drug, the investigator must maintain records of all study medication delivery to the site, site inventory, use by each patient, and return to the sponsor or designee.

Upon receipt of study medication, the investigator or designee must verify the contents of the shipments against the packing list. The verifier should ensure that the quantity is correct, the medication is received within the labelled storage conditions, and is in good condition. See pharmacy manual for receipt of shipments. If quantity and conditions are acceptable, investigator or designee should acknowledge the receipt of the shipment by signing bottom half of the packing list and notifying Santen per instructions provided on the form. If there are any discrepancies between the packing list versus the actual product received, Santen must be contacted to resolve the issue. The packing list should be filed in the investigator's essential document file.

The investigator must maintain 100% accountability for all study medication received and dispensed during his or her entire participation in the study. Proper drug accountability includes, but is not limited to:

- Continuously monitoring expiration dates if expiry date is provided to the investigator.
- Frequently verifying that actual inventory matches documented inventory.
- Verifying that the log is completed for the drug lot used to prepare each dose.
- Verifying that all containers used are documented accurately on the log.
- Verifying that required fields are completed accurately and legibly.

If any dispensing errors or discrepancies are discovered, the sponsor must be notified immediately.

The investigator must record the current inventory of all study medication on a sponsor-approved drug accountability log. The following information will be recorded at a minimum: protocol number and title, name of investigator, site identifier and number, description of study medication, expiry and/or retest date, date and amount dispensed, including the initials of the person dispensing and receiving the study medication. The log should include all required information as a separate entry for each patient to who study medication is dispensed.

Prior to site closure or at appropriate intervals, a representative from the sponsor or its designee will perform clinical study material accountability and reconciliation before clinical study materials are returned to the sponsor or its designee for destruction or destroyed at the site, as applicable. The investigator will retain the original documentation regarding clinical study

IKERVIS®	
Study NVG16E128	Page 38 of 93
Protocol Version 4.0	23 March 2018

material accountability, return, and/or destruction, and copies will be sent to the sponsor or designee.

The investigator will be notified of any expiry date or retest date extension of clinical study material during the study conduct. On expiry date notification from the sponsor or designee, the site must complete all instructions outlined in the notification, including segregation of expired clinical study material for return to the sponsor or its designee for destruction.

## 9.0 STUDY PLAN

## 9.1 Study Procedures

The following sections describe the study procedures and data to be collected. For each procedure, patients are to be assessed by the same investigator or site personnel whenever possible. The Schedule of Study Procedures is located in Appendix A-I.

## 9.1.1 Informed Consent Procedure

The requirements of the informed consent are described in Section 14.1.

Informed consent must be obtained prior to the patient entering into the study, and before any protocol-directed procedures are performed.

A unique patient identification number will be assigned to each patient at the time that informed consent is obtained; this patient number will be used throughout the study.

## 9.1.2 Demographics, Medical History, and Medication History Procedure

Demographic information to be obtained will include date of birth, sex, alcohol and smoking status of the patient at Screening.

Medical history to be obtained will include whether the patient has any significant conditions or diseases relevant to the condition/disease under study that stopped at or prior to informed consent. Ongoing conditions are considered concurrent medical conditions.

Medication history information to be obtained includes any medication relevant to eligibility criteria stopped at or within 1 year prior to signing of informed consent.

## 9.1.3 Safety Assessments

On Day 1, all the assessments must be reviewed by the investigator prior to study treatment initiation to assure eligibility requirements have been met. During the study, all assessments should be done prior to administration of study drug unless otherwise indicated.

## 9.1.4 Wash-out Period

During the 2-week wash-out phase all enrolled patients must discontinue all prior DED therapies including artificial tears and any prohibited ocular treatments. The sponsor will provide all patients with unpreserved artificial tears to use up to eight instillations per day in each eye the relief of their symptoms of DED. Patients will be instructed in the optimal technique for ophthalmic drop instillation.

## 9.1.5 Documentation of Concomitant Medications

Concomitant medication is any drug given in addition to the study medication. These may be prescribed by a physician or obtained by the patient over the counter. Concomitant medication is not provided by Santen. At each study visit, patients will be asked whether they have taken any

IKERVIS®	
Study NVG16E128	Page 40 of 93
Protocol Version 4.0	23 March 2018

medication other than the study medication (used from signing of informed consent through the end of the study), and all medication, including vitamin supplements, over-the-counter medications, and oral herbal preparations, must be recorded in the eCRF. Documentation will include generic medication name, dose, unit, frequency, route of administration, start and end dates, and reason for use.

## 9.1.6 Documentation of Concurrent Medical Conditions

Concurrent medical conditions are those significant ongoing conditions or diseases that are present at signing of informed consent. This includes clinically significant laboratory, ECG, or physical examination abnormalities noted at the Screening examination. The condition (ie.,. diagnosis) should be described.

## 9.1.7 Contraception and Pregnancy Avoidance Procedure

Women of childbearing potential not using a medically acceptable, highly effective method of birth control (such as hormonal implants, injectable or oral contraceptives together with condoms, some intrauterine devices, sexual abstinence or vasectomized partner) from the Screening Visit throughout the conduct of the study treatment periods and up to 2 weeks after the study end cannot be included in the study. Post-menopausal women (two years without menstruation) do not need to use any method of birth control.

IKERVIS®	
Study NVG16E128	Page 41 of 93
Protocol Version 4.0	23 March 2018

During the course of the study, urine hCG pregnancy tests will be performed only for women of childbearing potential and patients will receive continued guidance with respect to the avoidance of pregnancy as part of the Schedule of Study Procedures (Appendix A Schedule of Study Procedures and Procedures

Appendix -I). Patients must have a negative urine pregnancy test on Day 1 and throughout the study.

## 9.1.8 Pregnancy

If any patient is found to be pregnant during the study she should be withdrawn and any sponsorsupplied drug should be immediately discontinued. If the pregnancy occurs during administration of active study medication, the pregnancy should be reported within 14 days of completing the study

All reported pregnancies in a patient receiving active study medication will be followed up to final outcome, using the pregnancy form. The outcome, including any premature termination, must be reported to the sponsor. An evaluation after the birth of the child will also be conducted.

## 9.1.9 Documentation of Screen Failure

Investigators must account for all patients who sign informed consent. If the patient is found to be not eligible at Screening or Baseline visit, the investigator should complete the eCRF.

The primary reason for screen failure is recorded in the eCRF using the following categories:

- Pre-treatment event/AE.
- Did not meet inclusion criteria or did meet exclusion criteria.
- Major protocol deviation.
- Lost to follow-up.
- Voluntary withdrawal, specify reason.
- Study termination.
- Other, specify reason.

Patient numbers assigned to patients who fail screening should not be reused.

## 9.1.10 Documentation of treatment initiation

Only patients who meet all of the inclusion criteria and none of the exclusion criteria are eligible for treatment initiation into the treatment phase.

If the patient is found to be not eligible for treatment initiation, the investigator should record the primary reason for failure on the applicable eCRF.

IKERVIS®	
Study NVG16E128	Page 42 of 93
Protocol Version 4.0	23 March 2018

## 9.2 Monitoring Patient Treatment Compliance

Study medication will be administered on Day 1, Month 2 and Month 3. The date and time of each dose will be recorded in the source documents and on the eCRF. An inventory of the study medication supplies dispensed will be performed by the site pharmacist or authorized study designee and recorded onto the Drug Accountability Log in the patient's source document records or equivalent. If a patient is persistently noncompliant with the study medication, the patient might be withdrawn from the study. All patients should be reinstructed about the dosing requirement during study visits. The authorized study personnel conducting the re-education must document the process in the patient source records.

## 9.3 Schedule of Observations and Procedures

The schedule for all study-related procedures for all evaluations is shown in Appendix A-I. Assessments should be completed at the designated visit/time point(s).

The study period will include the initial Screening Visit, the 2-week wash-out phase, and the 3month open-label study treatment phase encompassing the Baseline, Month 1, 2 and 3 study visits. See Appendix A for details of procedures that will be performed and documented.

## 9.3.1 Screening

Patients will be screened for the study within 14 days prior to the first dose of study medication. Patients will be screened in accordance with predefined inclusion and exclusion criteria as described in Section 7.0. See Section 9.1.9 for procedures for documenting screening failures.

## 9.3.1.1 Screening Visit: Day $-14 \pm 3$ days

Procedures to be completed at Screening Visit include:

- Informed consent.
- Inclusion/exclusion criteria review.
- Demographics.
- Ocular and systemic medical history.
- Previous and concomitant ocular and systemic medications (including artificial tear usage).
- Visual Analogue Scales (0-100%, from 0 = no symptom, 100 = maximal symptom) to assess the severity photophobia and blurred vision (Appendix A-II).
- Uncorrected distance visual acuity (UDVA).
- Best corrected distance visual acuity (BCDVA, Appendix A-III).
- Functional visual acuity parameters (FVA, starting visual acuity, LogMAR FVA, VMR, and maximal and minimal visual acuities) using FVA measurement system (AS-28; Kowa, Aichi, Japan / Nidek, Gamagori, Japan) (Appendix A-IV).

- Ocular Scatter Index (OSI), using double-pass aberrometer (Optical Quality Analyzing System, Visiometrics, Spain) (Appendix A-V).
- Root mean square (RMS) of higher order aberrations (total, coma-like, spherical like) using Hartmann-Shack aberrometer (Appendix A-VI).
- Slit lamp examination (Appendix A-VII).
- Tear break up time (TBUT).
- Corneal fluorescein staining (CFS, modified Oxford scale) (Appendix A-VIII).
- Eligible patients will discontinue all previous treatments related to dry eye including artificial tears and any prohibited ocular treatments.
- Urine pregnancy test (women of childbearing potential only)
- Dispense unpreserved artificial tears.
- Initiate 1-2 week wash-out phase.
- Patients will be scheduled to return to the clinic in 14 days  $\pm 3$  days for the baseline visit.

## 9.3.2 Treatment Phase

All assessments should be done in the mentioned order to ensure that additional product doesn't interfere for the other result examinations.

## 9.3.2.1 Baseline: Day 1

- Inclusion/exclusion criteria review.
- Record Ocular and systemic medical history.
- Review of concomitant ocular and systemic concomitant medications (including artificial tear usage).
- Record adverse events (AEs)
- 0-100% VAS for photophobia and blurred vision severity
- UDVA
- BCDVA
- FVA parameters using FVA measurement system
- OSI using double-pass aberrometry system
- Slit lamp examination
- Dilated fundus examination
- TBUT

- CFS (modified Oxford scale)
- IOP
- Schirmer test (without anaesthesia)
- Urine pregnancy test (women of childbearing potential only)
- Collection of unpreserved artificial tear bottles (used/not used)
- Verify inclusion and exclusion criteria based on evaluations just performed:
  - Patients **fulfilling** the inclusion / exclusion criteria will receive the study treatment for the next month
  - Patients **not fulfilling** the inclusion / exclusion criteria will be discontinued from the study and the patient become screen failure (refer to section 9.1.9)
- Dispense study medication and unpreserved artificial tears for a 1-month period. Patients will be instructed on dosing of study medication.
- Patients will be scheduled to return to the clinic in 28 days  $\pm$  3 days for Month 1 visit.

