9.3.2.4 Month 3: Day 84 ±7 days

- Record concomitant ocular and systemic concomitant medications (including artificial tear usage)
- Record adverse events (AEs)
- Patient global evaluation of efficacy
- 0-100% VAS for photophobia and blurred vision severity
- UDVA
- BCDVA
- FVA parameters using FVA measurement system
- OSI using double-pass aberrometry system
- RMS of higher order aberrations using Hartmann-Shack aberrometer
- Slit lamp examination
- Dilated fundus examination

- TBUT
- CFS including assessment of complete corneal clearing (modified Oxford scale)
- IOP
- Schirmer test (without anaesthesia)
- Investigator global evaluation of efficacy
- Urine pregnancy test (women of childbearing potential only)
- Collection of study medication containers used/not used study medication containers and unpreserved artificial tear bottles.

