## 9.3.3 Unscheduled Visit/Premature Discontinuation

An unscheduled visit may be performed as needed between two scheduled visits. The reason for the visit will be recorded on the eCRF. The examinations required at an unscheduled visit will be at the discretion of the investigator.

If necessary, (e.g. to follow up an AE), the investigator may schedule further "unscheduled" visits at his/her discretion. Data from an unscheduled visit will not be collected in the eCRF with the exception of information related to an AE or the follow-up of an AE.

In case of premature study discontinuation between two scheduled visits, the Unscheduled Visit Form and the Exit Forms will be completed. If the premature discontinuation occurs during an Unscheduled Visit prior to Month 3, the investigator will complete and record all of the exams scheduled at the Month 3 Visit on the Unscheduled Visit Form. In case of premature study discontinuation, the investigator will ensure that all used and unused study medication for the study period has been collected from the patient.

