## 9.3.4.8 Schirmer Test (without anesthesia) (mm wetting/5min)

Schirmer test will be performed without anesthesia, 15 minutes after corneal fluorescein test. This test will be conducted in a dimly lit room. While the patient looks upwards, the lower lid will be drawn gently downwards and temporally. The rounded bent end of a sterile strip will be inserted into the lower conjunctival sac over the temporal one-third of the lower eyelid margin. The test should be done without touching directly the Schirmer test strip with the fingers to avoid contamination of skin oils. After 5 minutes have elapsed the Schirmer test strip is removed and the length of the tear absorption on the strip will be measured.

A positive change from baseline will indicate improvement.

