## 9.3.5.5 Tonometry for measurement of Intraocular Pressure (IOP) (mmHg)

IOP will be measured using Goldman applanation tonometry (one measurement), after instillation of one drop of oxybuprocaine 0.4% and fluorescein 0.5% solutions. IOP will be assessed after completion of all other slit lamp examinations and dry eye assessments to avoid oxybuprocaine interference with the other examinations (Schirmer test especially). The patient and slit lamp should be adjusted so that the patient's head is firmly positioned on the chin rest and against the forehead rest without leaning forward or straining. Both eyes will be tested, with the right eye preceding the left eye. The same equipment must be used throughout the course of the study. All equipment (i.e., slit lamp) should be calibrated and checked during monitoring visit.

IKERVIS®	
Study NVG16E128	Page 50 of 93
Protocol Version 4.0	23 March 2018

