4.2.2 Baseline Score

For any measure, the *baseline score* is the last observed measurement prior to the first dose of the study medication. If any variable is missing a value on Day 1, values from the Screening

Visit will be used to impute the baseline score, i.e., the last observation carried forward (LOCF) approach will be used.

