4.3.7 Schirmer Test (without Anaesthesia)

At the Baseline Visit (Day 1) and Month 3/premature study discontinuation visit, Schirmer test will be performed without anaesthesia to record the length of the tear absorption on the strip in 5 minutes. It will be recorded as mm wetting/5 min.

An increase from baseline in Schirmer test indicates improvement.

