6.2 Handling of Missing Data

6.2.1 Efficacy Endpoints

Missing observations on CFS, VMR, and variance of OSI will be imputed by the last-observation-carried-forward (LOCF) approach.

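### The Baseline and Month 3 lists place tonometry under oxybuprocaine just before a Schirmer test defined as unanaesthetised, against the protocol's own tonometry section

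*Protocol*

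**What the plan says.** Protocol 9.3.2 opens the treatment phase with an instruction on sequence and a reason for it: "All assessments should be done in the mentioned order to ensure that additional product doesn't interfere for the other result examinations". The lists at Baseline (9.3.2.1) and Month 3 (9.3.2.4) then both run TBUT, CFS, IOP, Schirmer test, with the Schirmer line itself marked as without anaesthesia.

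The procedure sections say something different. Under Protocol 9.3.5.5, IOP is measured after a drop of oxybuprocaine 0.4% with fluorescein 0.5%, and "IOP will be assessed after completion of all other slit lamp examinations and dry eye assessments to avoid oxybuprocaine interference with the other examinations"; a parenthesis singles out the Schirmer test. Protocol 9.3.4.8 states that "Schirmer test will be performed without anesthesia", 15 minutes after the fluorescein test, and does not mention IOP. SAP 4.3.7 repeats the condition: "At the Baseline Visit (Day 1) and Month 3/premature study discontinuation visit, Schirmer test will be performed without anaesthesia".

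**The concern.** The lists are presented as a working order whose purpose is to stop instilled products affecting later tests. For this one pair of tests, the listed order does the opposite. A site that works down the list gives an anaesthetic and then records a Schirmer value that does not meet its definition. A site that follows 9.3.5.5 departs from the list. If sites, or the two visits of one patient, differ, the change from baseline combines two measurement conditions.

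Schirmer is scheduled only at these two visits. A premature-discontinuation visit inherits the Month 3 examinations, since "the investigator will complete and record all of the exams scheduled at the Month 3 Visit". The results enter the descriptive summaries that SAP 8 plans for every measure in SAP 4.3, and two correlations of changes from baseline that SAP 10.4 reports as added: CFS with Schirmer, and LogMAR FVA with Schirmer.

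**Working it through.** The plan gives no figure to reproduce on this point. The check is a comparison of text, followed by a count of what depends on it.

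**Order of the two tests**

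| Source | What it implies |
|---|---|
| Protocol 9.3.2 | follow the listed order, to avoid product interference |
| Protocol 9.3.2.1 and 9.3.2.4 | IOP, then Schirmer |
| Protocol 9.3.5.5 | IOP uses oxybuprocaine and comes after all dry eye assessments |
| Protocol 9.3.4.8 | Schirmer unanaesthetised, 15 minutes after the fluorescein test; silent on IOP |
| Protocol Appendix A-I | Schirmer under efficacy, IOP under safety; does not order the two tests |
| SAP 4.3.7 | Schirmer unanaesthetised; silent on order |

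The second and third rows cannot both be followed. Neither list refers to 9.3.5.5, and no rule says which text prevails. A site following the list would perform IOP inside the 15-minute wait that 9.3.4.8 sets.

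**Readings involved**

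SAP 3.1 reports 17 enrolled patients, and there are two scheduled Schirmer visits: 17 × 2 = 34 analysis-eye readings and at most 17 change scores. This is a ceiling, because the protocol also uses the word enrolled for patients entering wash-out.

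**Share of the correlation analyses**

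Variable pairs in SAP 8.2.3.1: 14 with CFS + 9 with LogMAR FVA + 4 with OSI + 4 with variance of OSI = 31. Schirmer is in 2 of them. VMR, variance of OSI and CFS all come before IOP in both lists, so neither primary endpoint is touched.

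**If an affected reading is excluded**

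- SAP 4.2.2 provides that "If any variable is missing a value on Day 1, values from the Screening" Visit stand in, but Schirmer is not done at Screening (Protocol 9.3.1.1, Appendix A-I).
- SAP 6.2.1 says "Missing observations on CFS, VMR, and variance of OSI will be imputed by the last-observation-carried-forward (LOCF) approach", which leaves Schirmer out.

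Excluding a reading at either visit therefore loses that patient's change score.

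**Illustrative cost of exclusion**

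Assumptions: 17 patients spread evenly over 4 sites (17/4 ≈ 4 each), so dropping one site leaves 13 and dropping two leaves 9. The interval is tanh(atanh(r) ± 1.96/√(n − 3)), which is only approximate for a Spearman coefficient with ties.

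| n | 95% interval at r = 0.3 | width at r = 0 | width at r = 0.5 |
|---|---|---|---|
| 17 | −0.21 to 0.68 | 0.96 | 0.77 |
| 13 | −0.30 to 0.73 | 1.10 | 0.89 |
| 9 | −0.45 to 0.80 | 1.33 | 1.12 |

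For n = 17 at r = 0.3: atanh(0.3) = 0.310 and 1.96/√14 = 0.524, giving tanh(−0.214) = −0.21 and tanh(0.833) = 0.68.

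The table shows what exclusion costs in precision. It does not measure bias from the anaesthetic; the documents give no size for that effect and none is assumed.

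**The case against.** The strongest reply is that the protocol largely answers the question itself. Section 9.3.5.5 is the specific procedure text, it gives its reason, and the stated purpose in 9.3.2 points the same way. The Schirmer line in each list says without anaesthesia, so a careful site would notice. The lists also give way elsewhere: a footnote to Appendix A-I puts the VAS before medical history, although the Baseline list has history first. On this view it is a drafting slip affecting a measure that is not a listed endpoint, in an exploratory study with no formal hypothesis testing (SAP 8) and no multiplicity control (SAP 6.4).

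Much of this stands. The intended order can be recovered, little depends on Schirmer, and nothing shows that sites actually differed. A site that kept the listed order at both visits would have internally consistent change scores, though not of an unanaesthetised test. The correlations are imprecise even with all 17 patients. SAP section 1 says it applies to protocol version 3.0, whereas the visit lists reviewed here are in version 4.0, so some patients may have been examined under lists not available for this review. That is a further reason to treat 34 as a ceiling.

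It does not remove the contradiction. The listed order is itself an instruction, and the documents contain nothing from which the condition of any given Schirmer value can be known. The absence of a substitute value matters only if readings are excluded, but exclusion is one of the two natural ways to handle them.

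**Conclusion.** The concern holds. This is an internal inconsistency that should be corrected. At both scheduled Schirmer visits the listed order contradicts 9.3.5.5, and a site following the list would record a value that fails the definition in Protocol 9.3.4.8 and SAP 4.3.7. Up to 34 readings and 17 change scores are open to doubt, together with their summaries and two exploratory correlations. Whether any value was actually affected, and by how much, cannot be determined from the documents. The two primary correlations are not affected.

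**What to change.** Reconcile the lists in Protocol 9.3.2.1 and 9.3.2.4 with 9.3.5.5 and 9.3.4.8, so that they match the protocol's own rule that IOP follows the Schirmer test. This means exchanging two adjacent lines in each list.

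For patients already examined:

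- Establish from source documents, or by one query to each of at most 4 sites, which order was used at each visit.
- Flag Schirmer values taken after oxybuprocaine, or exclude them and report the remaining n.
- State the limitation beside the Schirmer summaries and the two correlations. If the order cannot be established, attach that statement to all Schirmer results.

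No test, staff or visit is added. The protocol does not ask sites to record examination order, so the query may fail at some of them. With 17 patients already reported as enrolled, the flag and the limitation statement are the main remedies still usable in this trial.

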9.3.2.2 Month 1: Day 28 ±3 days

- Record concomitant ocular and systemic concomitant medications (including artificial tear usage)
- Record adverse events (AEs)
- 0-100% VAS for photophobia and blurred vision severity
- UDVA
- BCDVA
- FVA parameters using FVA measurement system
- OSI using double-pass aberrometry system
- Slit lamp examination
- TBUT
- Corneal fluorescein staining (modified Oxford scale)
- Collection of used/not used study medication containers and unpreserved artificial tear bottles
- Dispense study medication and unpreserved artificial tears for a 1-month period (Month 1 Month 2)
- Patients will be scheduled to return to the clinic on Day  $56\pm3$  days for Month 2 visit.

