## 9.3.5.4 Dilated Fundus Examination

A dilated fundus examination will be performed after use of mydriatic eye drops to dilate the pupil in order to evaluate for posterior segment diseases. Abnormal outcomes will be described.

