4.4.2.4 Dilated Fundus Examination

A dilated fundus examination will be performed after the pupil is dilated at the Baseline and Month 3/early termination visits in order to evaluate for posterior segment diseases. It will be rated as normal or abnormal.

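### The listed assessment order puts mydriatic drops before TBUT and CFS at Baseline and Month 3 only, so Month 1 and Month 2 changes in CFS and TBUT compare unlike conditions

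*Protocol*

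**What the plan says.** Protocol section 9.3.2 opens the treatment phase with an instruction on sequence and its reason: "All assessments should be done in the mentioned order to ensure that additional product doesn't interfere for the other result examinations".

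The lists that follow differ by visit. At Baseline (9.3.2.1) and Month 3 (9.3.2.4) the entry "Dilated fundus examination" stands after the slit lamp examination and before TBUT and CFS. Section 9.3.5.4 says what it involves: "A dilated fundus examination will be performed after use of mydriatic eye drops to dilate the pupil". The Screening (9.3.1.1), Month 1 (9.3.2.2) and Month 2 (9.3.2.3) lists go straight from slit lamp to TBUT and CFS. The schedule in Protocol Appendix A-I agrees, and so does SAP section 4.4.2.4: "A dilated fundus examination will be performed after the pupil is dilated at the Baseline and Month 3/early termination visits".

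Protocol section 9.3.4.3 ties the CFS reading to the fluorescein instilled for TBUT, so whatever precedes TBUT also precedes CFS. Section 9.3.5.5 shields the dry-eye tests from one other drop: "IOP will be assessed after completion of all other slit lamp examinations and dry eye assessments to avoid oxybuprocaine interference". Nothing equivalent is said about the mydriatic, and no other section moves dilation to a later point in the visit.

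**The concern.** The stated purpose of the sequence is to keep one product from disturbing the next test, and the sequence does not serve it. Elsewhere the protocol treats recent drops as a threat to measurement. Artificial tears are barred for two hours before a visit (6.1, 7.3.3, 9.3.4.9), as is any topical treatment in the eligible eye (7.3.1), and tonometry is deferred because of its anaesthetic. Yet at two of the five visits a mydriatic goes in shortly before TBUT and CFS.

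The imbalance across visits matters more than the drop itself. Changes at Months 1 and 2 subtract a post-mydriatic baseline from an undilated value. FVA and OSI are measured before dilation everywhere, so only the CFS and TBUT side can move. One secondary objective (Protocol 5.1.2) is to compare the time course of CFS improvement with that of FVA and OSI. An artefact in one curve but not in the others bears directly on it.

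**Working it through.** **1. Order at each visit, from the Protocol lists**

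| Visit | Mydriatic before TBUT and CFS | Mydriatic before FVA and OSI |
|---|---|---|
| Screening (9.3.1.1) | no | no |
| Baseline (9.3.2.1) | yes | no |
| Month 1 (9.3.2.2) | no | no |
| Month 2 (9.3.2.3) | no | no |
| Month 3 (9.3.2.4) | yes | no |

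**2. Effect on mean changes.** Let D be the mean effect of the drops on the CFS grade. The documents give no value, so D is an assumption and could have either sign.

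- Month 1 or 2: observed change = true change − D.
- Month 3: observed change = true change + D(Month 3) − D(Baseline), which equals the true change if D is stable.

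For D = 0.25, 0.5 and 1.0 the bias at Months 1 and 2 is −0.25, −0.5 and −1.0 grade. With D negative the signs reverse. A simulation with D = 0.5 and 1.0 (between-patient SD 0.3, same effect within a patient at both dilated visits) returned Month 2 biases of about −0.50 and −1.00, and 0.00 at Month 3. The Month 3 zero follows from the assumed stability.

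For scale only, the protocol's two earlier trials (4.1.3) report drug–vehicle differences in mean CFS change of 1.81 − 1.48 = 0.33 and 1.05 − 0.82 = 0.23.

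**3. Effect on the time course.** Suppose the true mean changes are −1.0 at Month 2 and −1.3 at Month 3 (assumed). With D = 0.5 the plan would show −1.0 − 0.5 = −1.5 and then −1.3, an apparent loss of effect where there was further improvement. FVA and OSI would show no such turn.

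**4. Effect on the primary correlations.** Both use CFS change from Baseline to Month 3 (Protocol 5.2.1), two visits with the same order. Three routes remain.

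- LOCF (SAP 6.2.1) can put an undilated Month 1 or 2 CFS in place of Month 3. In the simulation (underlying correlation 0.5 in size, CFS-change SD 1.0, n = 17 and n = 30), the Spearman coefficient was unchanged with nothing missing (−0.464 both ways at n = 17 and −0.469 at n = 30, for D = 0.5). With 10–20% carried forward it moved by 0.001 to 0.017. CFS was treated as continuous with no ceiling at 5.
- A Screening value can replace a missing Baseline (SAP 4.2.2). This is the same kind of mismatch.
- The drop effect may vary within a patient between the two visits. With s the SD of CFS change, m the per-visit SD of the drop effect and r its within-patient correlation, the correlation shrinks by √(s² / (s² + 2m²(1 − r))). For s = 1.0 to 1.3 and m = 0.3 to 0.5 (assumed):
  - r = 0 gives √(1/1.5) = 0.82 to √(1.69/1.87) = 0.95, so 0.50 becomes 0.41 to 0.48.
  - r = 0.8 gives √(1/1.1) = 0.95 to √(1.69/1.726) = 0.99, so 0.50 becomes 0.48 to 0.49.

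With the 17 patients enrolled (SAP 3.1), a Fisher-z 95% interval around 0.50 is tanh(0.549 ± 1.96/√14) = tanh(0.549 ± 0.524), or 0.03 to 0.79. Sampling error swamps these shifts.

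**5. Other analyses.** A shift common to all patients leaves the ranks within each correlation unchanged, so same-visit and lagged Spearman coefficients do not move. The visit term in the sample mixed-model code (SAP Appendix B) absorbs it. A shift that varies between patients would not drop out of either. A common shift does not cancel in the Month 1–2 means, the CFS shift tables (SAP 8.2.2), the summaries by CFS-change category (SAP 8.1.2) or the mean plots (SAP 8.2.4).

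**The case against.** The strongest reply is that the documents never name the mydriatic, say that it alters staining or tear film, or give the interval before CFS is read. Every effect size above is assumed, and so is its direction. That stands. What the documents do establish is the unequal order and its conflict with its own stated purpose.

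A second reply is that the lists may not describe what sites did. The instruction is worded as advice, and because it opens 9.3.2 it does not formally cover Screening. The lists also clash with other text. They put IOP before Schirmer, against section 9.3.5.5, and the Baseline list puts the VAS after medical history, against the first footnote of Appendix A-I. This stands as a caution about data already collected. It also shows that the lists were not checked against the rules they should serve.

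A reader might infer that both primary endpoints are compromised because CFS enters each of them. The documents do not support this: the visits whose conditions differ do not enter the primary contrast. Nor does the 0.82 to 0.95 shrinkage describe the expected case, since it requires drop effects that are independent at two visits in the same patient. A reader might also infer that inflated Baseline grades let unsuitable patients in. Inclusion criterion 4 requires CFS 3 to 5 at Screening as well, so a Baseline shift cannot admit anyone graded below 3 there.

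Finally, the SAP (6.4, 8) calls the study purely exploratory and plans no formal hypothesis testing. That lowers the severity. It does not remove the problem, because describing the time course is one of the study's stated aims.

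**Conclusion.** The point holds as a measurement inconsistency that should be fixed, not as a threat to the primary analysis. Mean CFS and TBUT changes at Months 1 and 2, and the tables and plots built on them, carry the full mean effect of the mydriatic with its sign reversed. The comparison of the CFS time course with FVA and OSI inherits it on one side only. If the drops have no effect on staining or tear film, nothing is biased. If the effect is a quarter to half a grade, it is of the same order as the drug–vehicle differences the protocol quotes, although those come from six-month controlled trials and serve only as a yardstick.

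For the primary correlations a stable effect cancels. What remains, through LOCF, a substituted Screening value or visit-to-visit variation in the drop effect, is likely to be small beside the imprecision of 17 patients. These conclusions assume that the listed order was followed and that the drop effect is broadly stable within a patient.

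**What to change.** In Protocol sections 9.3.2.1 and 9.3.2.4, move the dilated fundus examination to the end of the examinations, after TBUT, CFS, Schirmer and IOP. Then no drop other than fluorescein precedes TBUT or CFS at any visit. In the same edit, reconcile the listed IOP-before-Schirmer order with section 9.3.5.5. The cost is a small edit to two lists, with no added procedure or visit. It cannot help patients already assessed, but it matters for any further use of these lists, including the follow-on study announced in Protocol 4.2.

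For data already collected, confirm with the sites which order was used. If it was the listed one, state in the SAP and the study report that Month 1 and Month 2 changes in CFS and TBUT compare undilated visits with a post-mydriatic baseline, and interpret the time course accordingly. This costs a sentence or two.

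A table using the undilated Screening CFS as reference for Months 1 and 2 is optional. Screening precedes withdrawal of prior dry-eye therapy, so the table must be labelled as confounded by the wash-out and cannot replace the main presentation.
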